8.2.4.2. Tumor Tissue Samples

Tissue collection will be required for biomarker research and enrollment into the study for patients in Part A (all cohorts) and Part B (ovarian cancer cohort only). For patients enrolled in Part A (all cohorts) and Part B (ovarian cancer cohort only) of the study, tissue will be required for PD-L1 biomarker and other exploratory analysis from a newly obtained core or excisional biopsy of a tumor lesion (should be taken only after study eligibility is confirmed) or from a recent biopsy defined by ≤ 3 years since last documented progression of disease will be required. For the NSCLC cohort, archived tissue should be submitted from a recent biopsy defined by ≤ 3 years old and this biopsy follows the most recent systemic therapy. If such an archived biopsy sample is not available, a new biopsy must be obtained for the patient to be eligible to participate in study. For all cohorts, new archived tissue will be obtained only if not restricted by local regulations.

In addition, an on-treatment study biopsy is required if any accessible lesions remain for Part A (all cohorts) and Part B (ovarian cancer cohort only). If clinically feasible, the biopsies should be taken from the same lesion. ~~Pretreatment and/or on treatment tumor tissue biopsies are optional for all Part B cohorts, except the ovarian cancer cohort, for which these biopsies are mandatory. Sites should confirm the availability of adequate tumor tissue with the site's pathology laboratory.~~ For patients enrolled to NSCLC cohort of Part B, the on-treatment biopsy is optional for whom newly obtained samples cannot be obtained such as in cases of inaccessibility or patient safety concern, an archived specimen following most recent systemic treatment should be submitted if not restricted by local regulations.

Sites must confirm the availability of adequate tumor tissue for the new biopsy from the site's pathology laboratory or adequate archived tumor tissue. Pretreatment formalin-fixed paraffin-embedded (FFPE) tumor tissue should be submitted in a whole block.

Attachment 1. Protocol JSCC Study Schedule

Assessments are to be performed at the times stipulated in the schedule and as clinically required in the management of the patient.

Screening/Baseline Assessments (Visit 0)

Relative Day Prior to Day 1 of Cycle 1	≤28	≤14	≤7	Comments
Written informed consent/assignment of patient identification number	X			ICF signed (prior to performance of any protocol-specific tests/procedures).
Review of eligibility criteria	X			
Medical history		X		
Physical examination		X		Full physical examination, including assessments of the head, eyes, ears, nose, and throat and the respiratory, cardiovascular, GI, urogenital, musculoskeletal, neurological, dermatological, hematologic/lymphatic, and endocrine systems.
Vital signs		X		BP, temperature, RR, and PR. Includes height (at baseline only) and weight.
ECOG performance status		X		
ECG (local)		X		Tripple ECG will be obtained, on which QTcF must be <470 ms (calculated from one ECG using Fridericia's Correction Formula and confirmed with 2 additional ECGs).
HIV screening (local)	X			Per institutional standards. If done within 28 days prior to Cycle 1, Day 1, as part of standard of care, does not need to be repeated prior to the start of Cycle 1.
Hematology (local)		X		Refer to Attachment 2.
Serum chemistry (central)		X		Refer to Attachment 2.
Urinalysis (local)		X		Refer to Attachment 2.
Coagulation (local)		X		Refer to Attachment 2. Obtain prior to tumor biopsy.
Thyroid function (central)		X		Refer to Attachment 2. Free T3 and free T4 will be measured only if TSH is abnormal or if there is clinical suspicion of an AE related to the endocrine system.
Pancreas function (central)		X		Refer to Attachment 2.
LVEF evaluation	X			Echocardiogram or MUGA scan.
Radiographic tumor assessment (CT/MRI)	X			If done within 28 d prior to Cycle 1, Day 1, as part of standard of care, does not need to be repeated prior to the start of Cycle 1.
Tumor measurement (palpable or visible)		X		
CTCAE v4.0 grading (preexisting conditions)		X		To be reported only after study eligibility is confirmed. Refer to Section 8.1.2.4 for reporting guidelines.
Concomitant medications		X		
Tumor markers (local)		X		As clinically indicated. For example, CEA in patients with colorectal cancer or CA125 in patients with ovarian cancer.

Relative Day Prior to Day 1 of Cycle 1	≤28	≤14	≤7	Comments
Tumor tissue biopsy		X		For Part A (all cohorts) and Part B (ovarian cancer cohort only): A newly obtained core or excisional biopsy of a tumor should be taken only after study eligibility is confirmed. For the NSCLC cohort in Part B a newly obtained core or excisional biopsy should be obtained if an archived tumor sample following the most recent systemic therapy is not available. Refer to the laboratory manual.
Archived tumor tissue	X			An archived tumor sample following most recent systemic treatment if not restricted by local regulations will be requested from all patients in Part B NSCLC cohort. If such an archived biopsy sample is not available, a new biopsy must be obtained for the patient to be eligible to participate in study. Refer to the laboratory manual.
Whole blood for biomarkers			X	Refer to the laboratory manual.
Pregnancy test (local)			X	Applies only to women of childbearing potential. Urine hCG or serum β -hCG is acceptable.

Abbreviations: AE = adverse event; BP = blood pressure; CA125 = cancer antigen 125; CEA = carcinoembryonic antigen; CT = computed tomography (scan); CTCAE = Common Terminology Criteria for Adverse Events; ECG = electrocardiogram; ECOG = Eastern Cooperative Oncology Group; GI = gastrointestinal; hCG = human chorionic gonadotropin; HIV = human immunodeficiency virus; ICF = informed consent form; LVEF = left ventricular ejection fraction; MRI = magnetic resonance imaging; MUGA = multigated acquisition (scan); PR = pulse rate; QTcF = QT interval corrected for heart rate using Fridericia's Correction Formula; RR = respiration rate; T3 = triiodothyronine; T4 = thyroxine; TSH = thyroid-stimulating hormone; v4.0 = Version 4.0 of CTCAE.

On-Study Treatment and Post-Treatment (Follow-Up) Assessments for Combination Therapy: LY3022855 plus Durvalumab

Note that a maximum of 12 months/26 doses of durvalumab treatment is permitted; last infusion at Week 50.

Screening procedures performed for safety within 72 hours prior to Cycle 1 Day 1 (C1D1) do not need to be repeated on C1D1.

Rows with *italicized* font indicate that there is no planned assessment for the time frame shown on the page.

LY3022855 plus Durvalumab Assessment (central or local laboratory indicated, if applicable)	Cycle 1 (Visit 1)						Comments Except for the Cycle 1, Day 1 visit, allowable windows are ± 3 days, unless otherwise indicated. On dosing days, all assessments to be performed preinfusion, unless stated otherwise.
	1	2	3	8	15	22	
Relative day within a 28-day cycle:							
Physical examination	X			X	X	X	Targeted physical examination (on the basis of clinical observations and symptomatology).
Vital signs	X			X	X	X	BP, temperature, RR, PR, and weight. Vital signs (BP, RR, and PR only) to be measured around infusions as follows (allowable window ± 10 min): Around each LY3022855 infusion: prior to, during (midway through), at the end, and 30 min after the end. Around each durvalumab infusion (based on a 60-min infusion): within 30 min prior to, during (approx. 30 min after start of infusion), and at the end (approx. 60 min after start of infusion). 1-h Observation period after durvalumab infusion: at 30 and 60 min after the end of the infusion (90 and 120 min after start of infusion) for the first durvalumab infusion only, and for subsequent infusions as clinically indicated. If the durvalumab infusion exceeds 60 min, monitoring of BP and PR should occur per the preceding principles or more frequently if clinically indicated.
ECOG performance status	X						
Pregnancy test (local)							Every 12 wk (± 7 d) after the first dose of study drug or according to local regulations or as clinically indicated, whichever is more frequent. Urine hCG or serum β-hCG.
ECG (local)	X						Single ECG. Obtain ECGs before any associated blood draws. On dosing days, ECG should be taken within 2 h prior to the start of the LY3022855 infusion and at least one time point 0-3 h after the durvalumab infusion. Additional ECGs to be obtained as clinically indicated.

LY3022855 plus Durvalumab Assessment (central or local laboratory indicated, if applicable)	Cycle 1 (Visit 1)						Comments Except for the Cycle 1, Day 1 visit, allowable windows are ± 3 days, unless otherwise indicated. On dosing days, all assessments to be performed preinfusion, unless stated otherwise.
	1	2	3	8	15	22	
Relative day within a 28-day cycle:							
Hematology (local)	X		X	X	X	X	Refer to Attachment 2.
Serum chemistry (local) - safety labs for dosing	X			X	X	X	Refer to Attachment 2. Results must be available and reviewed before administering study drug.
Serum chemistry (central)	X	X		X	X	X	Refer to Attachment 2.
Urinalysis (local)	X						Refer to Attachment 2. To be performed at Screening, at C1D1, and every 4 wk thereafter. Additional assessments as clinically indicated. Results need not be available before administering study drug.
Coagulation (local)							Refer to Attachment 2. As clinically indicated.
Thyroid function (central)	X						Refer to Attachment 2. Free T3 and free T4 will be measured only if TSH is abnormal or if there is clinical suspicion of an AE related to the endocrine system.
Pancreas function (central)							Refer to Attachment 2.
Tumor markers (local)							
Pharmacogenetic sample	X						Refer to the laboratory manual. Collect once. Sample can be collected at any time, if not collected on C1D1.

LY3022855 plus Durvalumab Assessment (central or local laboratory indicated, if applicable)	Cycle 1 (Visit 1)						Comments Except for the Cycle 1, Day 1 visit, allowable windows are ± 3 days, unless otherwise indicated. On dosing days, all assessments to be performed preinfusion, unless stated otherwise.
	1	2	3	8	15	22	
Relative day within a 28-day cycle:							
Immunogenicity	X					X	If at any time a patient experiences an IRR, attempt to obtain a blood sample for immunogenicity analysis as close to the onset of the event as possible, at the resolution of the event, and 30 d following the event. A portion of the sample taken for immunogenicity testing may be used for PK analysis.
Myoglobin (local)					X		Refer to Attachment 2. If serum CK Grade ≥ 2 , test for serum and urine myoglobin.
CTCAE v4.0 grading	X			X	X	X	Throughout study as needed. Refer to Section 8.1.1 for reporting guidelines.
Concomitant medications	X			X	X	X	Throughout study as needed.
LY3022855 administration	Refer to Table JSCC.1 for dose frequency during Part A.						For LY3022855 and durvalumab: Part A doses: Refer to Table JSCC.1.
Durvalumab administration	X				X		Part B doses and dose frequencies to be determined; refer to Section 7.2.2.2 for information.
Pharmacokinetics							
LY3022855 (predose on dosing days, unless noted otherwise)	X	X 2 h post-EOI C1D1 (± 1 h)	X 24 h post-EOI C1D1 (± 4 h)	X 48 h post-EOI C1D1 (± 4 h)	X	X	X The date and the time of all samples must be clearly and accurately recorded. EOI = end of infusion
Durvalumab (predose on dosing days, unless noted otherwise)	X	X Simultaneously with LY PK sample	X Simultaneously with LY PK sample	X Simultaneously with LY PK sample	X	X	X
Pharmacodynamics and tailoring							
Serum	X	X Simultaneously with LY PK sample	X Simultaneously with LY PK sample	X Simultaneously with LY PK sample	X	X	X Serum storage for correlative studies.
Plasma	X						Plasma storage for correlative studies.
Whole blood	X		X		X		Gene expression analysis and other exploratory research.
Flow cytometry							
Immunophenotyping #1	X			X	X	X	CD14 and CD16.
Immunophenotyping #2	X			X	X	X	TBNK & T cell subset/activation panels.
Immunophenotyping #3	X						MDSC panel.
Isoenzymes (central)							Refer to Attachment 2. Obtain at additional time points, as clinically indicated.

LY3022855 plus Durvalumab Assessment (central or local laboratory indicated, if applicable)	Cycle 1 (Visit 1)						Comments Except for the Cycle 1, Day 1 visit, allowable windows are ± 3 days, unless otherwise indicated. On dosing days, all assessments to be performed preinfusion, unless stated otherwise.
	1	2	3	8	15	22	
Relative day within a 28-day cycle:	1	2	3	8	15	22	
LVEF evaluation							Echocardiogram or MUGA scan. Obtain at additional time points, as clinically indicated.
Radiographic tumor assessment (CT/MRI)							Perform every 8 wk (± 7 d), starting on Cycle 2, Day 22.
Tumor measurement (palpable or visible)							
Tumor biopsy							For Part A (all cohorts) and Part B (ovarian cancer cohort only): An on-treatment tumor core needle or excisional biopsy to be performed 6-8 wk after starting study treatment.

LY3022855 plus Durvalumab Assessment (central or local laboratory indicated, if applicable)	Cycle 2 (Visit 2)						Comments Except for the Cycle 1, Day 1 visit, allowable windows are ± 3 days, unless otherwise indicated. On dosing days, all assessments to be performed preinfusion, unless stated otherwise.
	1	8	9	10	15	22	
Relative day within a 28-day cycle:							
Physical examination	X	X			X	X	Targeted physical examination (on the basis of clinical observations and symptomatology).
Vital signs	X	X			X	X	
BP, temperature, RR, PR, and weight.
 
Vital signs (BP, RR, and PR only) to be measured around infusions as follows (allowable window ± 10 min):
 
Around each LY3022855 infusion: prior to, during (midway through), at the end, and 30 min after the end.
 
Around each durvalumab infusion (based on a 60-min infusion): within 30 min prior to, during (approx. 30 min after start of infusion), and at the end (approx. 60 min after start of infusion).
 
1-h Observation period after durvalumab infusion: at 30 and 60 min after the end of the infusion (90 and 120 min after start of infusion) as clinically indicated.
 
If the durvalumab infusion exceeds 60 min, monitoring of BP and PR should occur per the preceding principles or more frequently if clinically indicated.

ECOG performance status	X						
Pregnancy test (local)							Every 12 wk (± 7 d) after the first dose of study drug or according to local regulations or as clinically indicated, whichever is more frequent. Urine hCG or serum β-hCG.
ECG (local)	X						Single ECG. Obtain ECGs before any associated blood draws. ECG should be taken within 2 h prior to the start of the LY3022855 infusion and at least one time point 0-3 h after the durvalumab infusion. Additional ECGs to be obtained as clinically indicated.
Hematology (local)	X	X			X	X	Refer to Attachment 2.
Serum chemistry (local) - safety labs for dosing	X	X			X	X	Refer to Attachment 2. Results must be available and reviewed before administering study drug.
Serum chemistry (central)	X	X			X	X	Refer to Attachment 2.
Urinalysis (local)	X						Refer to Attachment 2. To be performed at Screening, at C1D1, and every 4 wk thereafter. Additional assessments as clinically indicated. Results need not be available before administering study drug.
Coagulation (local)	X						Refer to Attachment 2. Obtain prior to tumor biopsy. Additional assessments as clinically indicated.

LY3022855 plus Durvalumab Assessment (central or local laboratory indicated, if applicable)	Cycle 2 (Visit 2)						Comments Except for the Cycle 1, Day 1 visit, allowable windows are ± 3 days, unless otherwise indicated. On dosing days, all assessments to be performed preinfusion, unless stated otherwise.
	1	8	9	10	15	22	
Relative day within a 28-day cycle:							
Thyroid function (central)	X						Refer to Attachment 2. Free T3 and free T4 will be measured only if TSH is abnormal or if there is clinical suspicion of an AE related to the endocrine system.
Pancreas function (central)	X						Refer to Attachment 2.
Tumor markers (local)	X						If clinically indicated.
Pharmacogenetic sample							Refer to the laboratory manual. Collect once. Sample can be collected at any time, if not collected on C1D1.
Immunogenicity		X					If at any time a patient experiences an IRR, attempts to obtain a blood sample for immunogenicity analysis as close to the onset of the event as possible, at the resolution of the event, and 30 days following the event. A portion of the sample taken for immunogenicity testing may be used for PK analysis.
Myoglobin (local)	X	X			X	X	Refer to Attachment 2. If serum CK Grade ≥ 2 , test for serum and urine myoglobin.
CTCAE v4.0 grading	X	X			X	X	Throughout study as needed. Refer to Section 8.1.1 for reporting guidelines.
Concomitant medications	X	X			X	X	Throughout study as needed.
LY3022855 administration	Refer to Table JSCC.1 for dose frequency during Part A.						For LY3022855 and durvalumab: Part A doses: Refer to Table JSCC.1. Part B doses and dose frequencies to be determined; refer to Section 7.2.2.2 for information.
Durvalumab administration	X				X		
Pharmacokinetics							
LY3022855 (predose on dosing days, unless noted otherwise)	X	X	X 2 h post-EOI C2D8 (± 1 h)	X 24 h post-EOI C2D8 (± 4 h)	X 48 h post-EOI C2D8 (± 4 h)	X	The date and the time of all samples must be clearly and accurately recorded. EOI = end of infusion
Durvalumab (predose on dosing days, unless noted otherwise)	X	X	X Simultaneously with LY PK sample	X Simultaneously with LY PK sample	X Simultaneously with LY PK sample	X	
Pharmacodynamics and tailoring							
Serum	X	X	X Simultaneously with LY PK sample	X Simultaneously with LY PK sample	X Simultaneously with LY PK sample	X	Serum storage for correlative studies.
Plasma			X				Plasma storage for correlative studies.
Whole blood	X				X		Gene expression analysis and other exploratory research.
Flow cytometry							
Immunophenotyping #1	X	X			X		CD14, CD16.
Immunophenotyping #2	X	X			X		TBNK & T cell subset/activation panels.
Immunophenotyping #3	X						MDSC panel.

LY3022855 plus Durvalumab Assessment (central or local laboratory indicated, if applicable)	Cycle 2 (Visit 2)						Comments Except for the Cycle 1, Day 1 visit, allowable windows are ± 3 days, unless otherwise indicated. On dosing days, all assessments to be performed preinfusion, unless stated otherwise.
	1	8	9	10	15	22	
Relative day within a 28-day cycle:							
Isoenzymes (central)	X						Refer to Attachment 2. Obtain at additional time points, as clinically indicated.
LVEF evaluation						X	Echocardiogram or MUGA scan. Obtain at additional time points, as clinically indicated.
Radiographic tumor assessment (CT/MRI)						X	Perform every 8 wk (± 7 d), starting on Cycle 2, Day 22.
Tumor measurement (palpable or visible)						X	
Tumor biopsy		X					For Part A (all cohorts) and Part B (ovarian cancer cohort only): An on-treatment tumor core needle or excisional biopsy to be performed 6-8 wk after starting study treatment; that is, at Cycle 2, between Days 8 and 22. For Part B (NSCLC cohort) an optional on-treatment tumor tissue should be collected from patients in the study where possible.

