Patients in Part B will be treated at the MTD identified for LY3022855 in combination with durvalumab in Part A, unless otherwise specified by the sponsor.

Key Study Definitions

enter: Patients who are entered in the trial are those who have signed the informed consent form directly or through their legally acceptable representatives.

enroll: Patients who are enrolled in the trial are those who have been assigned to a treatment and have received at least 1 dose of study treatment.

interim analysis: An analysis of clinical study data that is conducted before the final reporting database is authorized for data lock.

study completion: This study will be considered complete when the primary and secondary objectives have been met.

continued access period: The period between study completion and end of trial during which patients on study treatment who continue to experience clinical benefit and no undue risks may continue to receive study treatment until one of the criteria for discontinuation is met.

end of trial: End of trial is the date of the last visit or last scheduled procedure for the last patient.

Notable Statistical Methods:

The analyses for this study will be descriptive; no p values will be calculated. Data analyses will be provided by cohort and treatment, whenever appropriate. For continuous variables, summary statistics will include the number of patients, mean, median, standard deviation, minimum, and maximum. Categorical endpoints will be summarized using the number of patients and percentages. Missing data will not be imputed.

Tumor response data, according to RECIST 1.1, will be tabulated by cohorts. Particularly, the antitumor effect will be summarized by best overall response, including the overall response rate (ORR) and disease control rate (DCR; complete response [CR]+ partial response [PR]+ stable disease [SD]).

3. Table of Contents

A Phase 1a/1b Trial Investigating the CSF-1R Inhibitor LY3022855 in Combination with Durvalumab (MEDI4736) or Tremelimumab in Patients with Advanced Solid Tumors

Section	Page
1. Protocol I5F-MC-JSCC(c) A Phase 1a/1b Trial Investigating the CSF-1R Inhibitor LY3022855 in Combination with Durvalumab (MEDI4736) or Tremelimumab in Patients with Advanced Solid Tumors	1
2. Synopsis	2
3. Table of Contents	8
4. Abbreviations and Definitions	15
5. Introduction	21
5.1. Rationale and Justification for the Study	21
5.1.1. Summary of the Rationale for Amendment (a)	21

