6.1.1. Inclusion Criteria

Patients may be included in the study if they meet all of the following criteria during screening prior to first dose of study drug.

(Note: If a specific cohort is not indicated for a criterion, the criterion applies to all patients.)

- [1] Must have histological or cytological evidence of a diagnosis of cancer that is not amenable to curative therapy.
- [2] Part B (all cohorts): Must have a type of malignancy that is being studied, as listed in the following:
 - [a] LY3022855 and durvalumab (MEDI4736) combination cohorts
 - [i] NSCLC that has relapsed or is refractory (definitions below) to immune checkpoint inhibitor therapy and has progressed through no more than 3 lines of therapy (one line must have been a platinum-containing regimen).
 - Relapsed: Following initial clinical benefit (that is, complete response [CR], partial response [PR], or stable disease [SD] on any scan), patients must have documented radiographic disease progression while receiving therapy with an immune checkpoint inhibitor.
 - Refractory: Patients must have documented radiographic disease progression ≤ 16 weeks after the start of treatment with an immune checkpoint inhibitor, with no evidence of clinical benefit (that is, CR, PR, or SD on any scan) while receiving therapy.

- a. Patients must not have a known activating mutation of the *EGFR* or *ALK* gene. If a site uses algorithmic testing that has eliminated the possibility of *EGFR* or *ALK* gene mutations, no specific testing for mutations in these genes is required.
- b. Patients could have received only one prior immune checkpoint therapy (anti-PD-1/PD-L1 or anti-CTLA-4, or a single regimen combining anti-PD-1/PD-L1 with an anti-CTLA-4).

[ii] Ovarian cancer (epithelial ovarian cancer, fallopian tube cancer, or primary peritoneal cancer) that has been treated with no more than 3 lines of therapy (with or without platinum).

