Abbreviations: ALT = alanine aminotransferase; ANC = absolute neutrophil count; aPTT = activated partial thromboplastin time; AST = aspartate aminotransferase; GFR = glomerular filtration rate; INR = international normalized ratio; PT = prothrombin time; PTT = partial thromboplastin time; T4 = thyroxine; TSH = thyroid-stimulating hormone; ULN = upper limit of normal.

^a GFR should be estimated via the Chronic Kidney Disease Epidemiology Collaboration (CKD-EPI) creatinine equation (Levey et al. 2009).

[8] Have a performance status of ≤ 1 on the Eastern Cooperative Oncology Group (ECOG) scale (refer to [Attachment 5](#)).

[9] Have discontinued previous treatments for cancer and recovered from the acute effects of therapy.

At the discretion of the investigator, patients with hormone-refractory prostate cancer who are stable on gonadotropin-releasing hormone (GnRH) agonist therapy or maintenance prednisone, and patients with breast cancer who are stable on antiestrogen therapy (for example, an aromatase inhibitor) may have that treatment continued while they are enrolled.

[10] Are reliable and willing to make themselves available for the duration of the study and are willing and able to comply with the protocol for the duration of the study, including undergoing treatment, scheduled visits and examinations (including follow-up), and attempted pretreatment and on-treatment tumor biopsies (Part A – all cohorts and Part B – ovarian cancer cohort only).

[11] Have an estimated life expectancy, in the judgment of the investigator, of at least 12 weeks.

[12] Male patients:

[a] who are sterile (including vasectomy)

or

[b] who are not sterile and agree to use 2 acceptable methods of effective contraception* during the study, starting at screening, for at least 6 months following last dose of study drug(s); and agree not to donate sperm during the study and for at least 6 months following last dose of study drug

[13] Female patients:

[a] are women not of childbearing potential due to surgical sterilization (at least 6 weeks postsurgical bilateral oophorectomy with or without hysterectomy or tubal ligation) confirmed by medical history, or postmenopausal by history. Postmenopausal women include women with either:

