6.1.2. Exclusion Criteria

Potential study patients may not be included in the study if any of the following apply during screening.

- [14] Have received treatment with an investigational product or nonapproved use of a drug or device (other than the study drug used in this study) within 28 days prior to the initial dose of study drug, or are concurrently enrolled in any other type of medical research judged not to be scientifically or medically compatible with this study.
- [15] Have been involved in the planning and/or conduct of the study (applies both to sponsor staff and/or to staff at the study site) or have an immediate family member (for example, spouse, parent/legal guardian, sibling, or child) who is investigational site or sponsor staff directly involved with this trial, unless prospective institutional review board (IRB) approval (by chair or designee) is obtained, allowing exception to this criterion for a specific patient.
- [16] Have previously been enrolled in the present study.
- [17] Have had any of the following anticancer therapies prior to enrollment:
 - [a] small molecule therapy or chemotherapy within 14 days.
 - [b] radiation therapy within 14 days.
 - [c] monoclonal antibody treatment within 28 days.
- [18] Are currently receiving or have had prior use of immunosuppressive medication within 28 days before the first dose of study drug, with the exception of intranasal and inhaled corticosteroids or systemic corticosteroids at physiological doses, which are not to exceed 10 mg/day of prednisone, or an equivalent corticosteroid.
- [19] Have had major surgery within 28 days prior to enrollment.
- [20] Have a serious preexisting medical condition, including, but not limited to, the following:
 - [a] Known human immunodeficiency virus (HIV) infection or acquired immunodeficiency syndrome (AIDS)-related illness (baseline screening required within 28 days prior to enrollment).
 - [b] History of immunodeficiency (primary and secondary).
 - [c] Active or prior documented autoimmune disease within the past 24 months. NOTE: Patients with vitiligo, Graves disease, or psoriasis not requiring systemic treatment (within the past 24 months) are not excluded.
 - [d] Active or prior documented inflammatory bowel disease (for example, Crohn's disease, ulcerative colitis).

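### The baseline CT/MRI may precede the last prior chemotherapy, small-molecule or radiotherapy dose by up to 13–14 days, so tumor change from that therapy can be credited to the study combination

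*Protocol*

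**What the plan says.** **Scan.** In the protocol's Attachment 1, the screening row for radiographic tumor assessment sets a window of up to 28 days before Cycle 1 Day 1 and adds: "If done within 28 d prior to Cycle 1, Day 1, as part of standard of care, does not need to be repeated". Attachment 10 only reproduces this row. Section 8.3 also lets scans older than 28 days be used in rare circumstances, after documented discussion with the sponsor.

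**Washout.** Exclusion 17 (section 6.1.2) begins "Have had any of the following anticancer therapies prior to enrollment" and lists "small molecule therapy or chemotherapy within 14 days", "radiation therapy within 14 days" and "monoclonal antibody treatment within 28 days". The synopsis defines enrolled patients as those who "have been assigned to a treatment and have received at least 1 dose of study treatment". The washout and the scan window therefore count back from the same date.

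**Order of scan and prior therapy.** Inclusion 9 requires that patients "Have discontinued previous treatments for cancer and recovered from the acute effects of therapy", but sets no order relative to the scan. The SAP (Table JSCC.6.1) takes as baseline the last measure before first dose. SAP section 6.13 has no rule for anticancer therapy given between the baseline scan and the first dose.

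**Eligibility.** The ovarian criterion (inclusion 2) asks only for disease "that has been treated with no more than 3 lines of therapy (with or without platinum"). It does not ask for progression on the last line. Part A has no such requirement either.

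**The concern.** A RECIST baseline should describe the tumor as it stood when prior treatment ended and study treatment was about to begin. Here the scan may be up to 28 days old while three classes of prior therapy need stop only about 14 days before dosing. A patient could be scanned, receive a further dose of chemotherapy or a course of radiotherapy to a measured lesion, wait out the washout and start study drug. Shrinkage from that last treatment would then be measured from the early scan and read as an effect of LY3022855 plus its partner.

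The cohorts are single-arm, so no control group carries the same artifact. What is at stake is the antitumor-activity objective: the overall response rate (ORR) and disease control rate (DCR), each reported with an exact 95% interval (protocol section 10.8). Response precision is also one of the stated reasons for 20 patients per Part B cohort (section 10.1).

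The protocol applies the missing principle elsewhere. Archived NSCLC tissue must post-date the most recent systemic treatment (inclusion 3, section 8.2.4.2). The antibody washout equals the scan window, so antibodies leave no gap.

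**Working it through.** **Inputs.** Scan window 28 days (Attachment 1). Washout 14 days for chemotherapy, small molecules and radiotherapy, and 28 days for antibodies (exclusion 17). First on-study scan at Cycle 2 Day 22, ±7 days (Attachment 1). Confirmation at least 8 weeks after the first observation of response (section 8.3). Cohort size 20 and Clopper-Pearson intervals (section 10.1).

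**1. The plan's own figure.** Limits are the 0.025 quantile of Beta(x, n−x+1) and the 0.975 quantile of Beta(x+1, n−x), with the lower limit 0 when x = 0. For n = 20:

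- x = 0: 0.000–0.168
- x = 5: 0.087–0.491
- x = 10: 0.272–0.728
- x = 15: 0.509–0.913

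After rounding, all agree with Table JSCC.5.

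**2. Permitted overlap.** Scan window minus washout:

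- Chemotherapy, small molecules, radiotherapy: 28 − 14 = 14 days. If Day −14 itself is barred, the last permitted day is Day −15 and the gap is 28 − 15 = 13 days.
- Antibodies: 28 − 28 = 0 days.

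A scan older than 28 days, accepted under section 8.3, would widen the gap.

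**3. How long a carried-over response must last to count in ORR.** Cycle 2 Day 22 is study day 28 + 22 = 50, which is 49 days after Cycle 1 Day 1, or 42 days at the early edge of the window. From the last prior dose to the earliest confirmation:

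- early edge: 14 + 42 + 56 = 112 days = 16 weeks
- nominal: 14 + 49 + 56 = 119 days = 17 weeks

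Confirmation therefore screens out short-lived shrinkage but not durable shrinkage, because the confirming scan is compared with the same early baseline.

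**4. DCR.** Section 10.8 attaches confirmation to complete and partial response only. A lesion that shrank before dosing and regrew on study to about its size on the early scan could read as stable, and the patient would count in DCR.

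**5. Size per event.** One misattributed response in 20 adds 1/20 = 5 points. ORR moves from 0/20 (95% CI 0–16.8%) to 1/20 = 5% (0.1–24.9%). No rate of such events can be computed from the documents.

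**6. After the fix.** If the scan must follow the last prior dose, the overlap is 0 days. Sample size and Table JSCC.5 do not change.

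**The case against.** **Confirmation.** A reader might infer that any shrinkage from prior therapy will count as a response. That does not hold: only confirmed responses enter ORR, and step 3 shows the shrinkage must last about 16 weeks or more from the last prior dose. This narrows the ORR concern considerably. It leaves DCR untouched.

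**The pre-dose share of the interval.** With a Day −28 scan, 28 of the 28 + 49 = 77 days to the first on-study scan (36%) precede study drug, and growth in that time can look like early progression. A reader might count this as part of the defect. It is not: it holds for any early scan, including in patients long off treatment, and comes from the 28-day window, which the fix keeps.

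**Frequency.** A reader might assume a share of patients with the wrong order and treat it as a share of false responses. The documents support neither. A false response needs an early scan, therapy after it, enough shrinkage to qualify, and persistence to confirmation.

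**Reach.** Part B NSCLC patients need documented radiographic progression on a checkpoint inhibitor, though not necessarily on their last line, so they are less exposed. Palpable or visible lesions are measured within 14 days of dosing. Exclusion 26 gives investigators discretion, prior therapies and lesion measurements are listed (SAP sections 6.5 and 6.13), and images may be requested for central review. A suspect response may therefore be found in a small listing, but no rule says what to do with it.

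**Irradiated lesions.** The documents defer to RECIST 1.1, which is not reproduced in them, so their silence does not prove that such lesions are ungoverned. The radiotherapy part is a clarification.

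**Importance.** Antitumor activity is a secondary objective, analyses are descriptive, Table JSCC.5 is expressly not a basis for decisions, and the recommended dose rests on tolerability. All of this stands and limits the weight of the point.

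**Conclusion.** The gap is real. The documents allow 13–14 days of chemotherapy, small-molecule treatment or radiotherapy after the scan that becomes the baseline, and nothing in the protocol or SAP closes it. The exposure lies mainly in the ovarian cohort and Part A. For ORR it is limited by the confirmation rule; for DCR, stable disease has no such protection.

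The size is 5 percentage points of ORR per misattributed response in a 20-patient cohort, with the frequency unknown. The reading assumes that enrollment in exclusion 17 carries its defined meaning of first dose, and that an accepted standard-of-care scan is used as the RECIST baseline. The importance is modest because the endpoints are secondary and descriptive. The change is worth making because it is specific and cheap.

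**What to change.** **Protocol.** In the Attachment 1 screening row and in section 8.3, accept a baseline scan, standard of care or study, only if it was done after the last dose of prior anticancer therapy, including radiotherapy. Apply the same condition to the section 8.3 exception for scans older than 28 days, so that the two places agree. State that a lesion irradiated after the baseline scan may not be a target lesion.

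**SAP.** For patients already enrolled, flag in section 6.13 those whose baseline scan preceded their last prior therapy, and report ORR and DCR with and without them. The flag needs only the scan date and the date of last prior treatment; sites need the latter to check exclusion 17.

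**Cost.** A few standard-of-care scans must be timed later in the window or repeated. No patients are added. The rule reduces the problem but does not fully remove it: a scan taken one day after the last prior dose would comply, and delayed effects of that dose could still be credited to the combination.
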